6.2 Secondary Efficacy Endpoints

Secondary efficacy endpoints for include:

1. Percent of subjects with new HO at Months 12, 24, 36, and overall.
2. Change from baseline in ROM as assessed by CAJIS at Months 6, 12, 18, 24, 30, and 36.
3. Change from baseline in physical function using age-appropriate forms of the FOP-PFQ at Months 6, 12, 18, 24, 30, and 36.
4. Change from baseline in physical and mental function for subjects ≥ 15 years old and mental function for subjects < 15 years old using age-appropriate forms of the PROMIS Global Health Scale at Months 6, 12, 18, 24, 30, and 36.

Secondary endpoints will also be summarized before the pause in palovarotene dosing and after restarting palovarotene.

6.2.1 New HO

The presence of new HO at each scheduled visit will be determined by low-dose WBCT scan, excluding head. Note that “New HO” means new HO compared to baseline. Baseline will be based on assessment from WBCT prior to the start of Non-flare-up dosing in Part B or Part C.

The presence of “HO at baseline” and the incidence of “No new HO”, and “New HO” will be summarized with counts and percentages overall and by regions.

6.2.2 Cumulative Analogue Joint Involvement Scale (CAJIS)

Range of motion across the whole body will also be assessed using the CAJIS.

The assessments will be performed on 12 joints (shoulder, elbow, wrist, hip, knee, and ankle on both the right and left sides), and three body regions (jaw, cervical spine [neck], and thoracic/lumbar spine). Each joint/region will be scored as: 0 = uninvolved; 1 = partially involved; and 2 = ankylosed/completely involved.

The CAJIS Total score will be calculated as the sum of the scores of all joints/regions and ranges from 0 (no involvement) to 30 (maximally involved).

The CAJIS Upper Extremities subscore will be calculated as the sum of the scores from six joints (shoulder, elbow, and wrist on both the right and left sides) and one region (cervical spine [neck]) and ranges from 0 (no involvement) to 14 (maximally involved).

The CAJIS Mobility subscore will be calculated as the sum of scores from six joints (hip, knee, and ankle on both the right and left sides) and ranges from 0 (no involvement) to 12 (maximally involved).

The CAJIS Total score, CAJIS Upper Extremities subscore, and CAJIS Mobility subscore and changes from baseline (defined in Section 3.1) will be summarized at each scheduled visit with descriptive statistics.

6.2.3 FOP-Physical Function Questionnaire (FOP-PFQ)

Age-appropriate forms of the FOP-PFQ will be administered to subjects (or parent proxy). The adult form will be administered to subjects 15 years and older. For subjects between 8 and 14 years of age, both the pediatric self-completed and the pediatric proxy-completed forms will be administered. The proxy-completed form will be used for analyses unless only the self-completed form is available.

The FOP-PFQ consists of 28 questions on the adult form and 26 questions on the pediatric form scored on a scale from 1 to 5, with lower scores indicating more difficulty. The questions are described in detail in Appendices 2A, 2B, and 2C of the protocol.

The Total score will be calculated as:

- The sum of the scores from each question and ranges from $28 \times 1 = 28$ to $28 \times 5 = 140$ for the adult form.
- The sum of the scores from each question and ranges from $26 \times 1 = 26$ to $26 \times 5 = 130$ for the pediatric form.

The Upper Extremities subscore will be calculated as:

- The sum of the scores from 15 questions (questions 1, 2, 3, 4, 5, 6, 7, 8, 9, 10, 11, 12, 14, 25, and 26) and ranges from $15 \times 1 = 15$ to $15 \times 5 = 75$ for the adult form.
- The sum of the scores from 18 questions (questions 1, 2, 6, 7, 8, 9, 10, 11, 16, 17, 18, 19, 21, 22, 23, 24, 25, and 26) and ranges from $18 \times 1 = 18$ to $18 \times 5 = 90$ for the pediatric form.

The Mobility subscore will be calculated as:

- The sum of the scores from 13 questions (questions 13, 15, 16, 17, 18, 19, 20, 21, 22, 23, 24, 27, and 28) and ranges from $13 \times 1 = 13$ to $13 \times 5 = 65$ for the adult form.
- The sum of the scores from 8 questions (questions 3, 4, 5, 12, 13, 14, 15, and 20) and ranges from $8 \times 1 = 8$ to $8 \times 5 = 40$ for the pediatric form.

The Total score, Upper Extremities subscore, and Mobility subscore are defined based on information from PROMIS and Hays et al (2013)¹ for the adult form and a medical review of the questions for the pediatric form.

If a subject is missing some (but not more than 20%) of the contributing question scores, the Total score, Upper Extremities subscore, or Mobility subscore will be calculated as the average observed score multiplied by the number of expected question scores. For example, the Total score would be calculated as the average of the non-missing scores $\times 28$ for the adult form. The determination for sufficient non-missing scores will be made independently for the Total score, Upper Extremities subscore, and Mobility subscore.

As the analysis for FOP-PFQ will be performed across all subjects (adult and pediatric) and the number of contributing questions differs, the scores will be transformed to reflect a percentage of worst score. The percentage of worst score ranges from 0% to 100% with 0% indicating the best possible function and 100% indicating the worst possible function. Table 2 illustrates some sample derivations of the percentage of worst score.

Table 2: Sample Derivations for the Percentage of Worst Score for the FOP-PFQ

Sample Subject	Observed FOP-PFQ Score	Lowest Possible Score	Highest Possible Score	Range of Possible Scores	Distance = Highest - Observed	Distance/Range	Percentage of Worst Score
1	45	15	75	60	30	0.500	50.0%
2	40	15	75	60	35	0.583	58.3%
3	35	15	75	60	40	0.667	66.7%
4	30	15	75	60	45	0.750	75.0%
5	25	15	75	60	50	0.833	83.3%

Percentage of worst scores and changes from baseline (defined in Section 3.1) of will be summarized at each scheduled visit with descriptive statistics.

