2.2 Study Design

PVO-1A-202 Part C is a Phase 2, multicenter, open-label extension of Study PVO-1A-202 Part B. This continuation of the open-label extension study will give subjects who participated in Part B the opportunity to be followed for up to an additional 36 months. There will be no new subjects in Part C.

Part D annual post last dose of study treatment assessments for up to 2 years will be obtained in subjects who were skeletally immature at the time of study treatment discontinuation in order to obtain longer-term safety data. No new subjects will be enrolled in Part D. Subjects will follow assessments outlined in Table 4 of the protocol as long as they are not 100% skeletally mature. Part C plus Part D total duration will not exceed 48 months.

Added assessments for spinal health will be carried out on low dose WBCT scans collected in the study.

Non Flare-up Based Treatment

Subjects will follow all procedures and undergo all assessments as specified in the Schedule of Assessments in Table 1 and Table 2 of the protocol. Subjects who cannot receive non-flare-up based treatment will only undergo annual assessments (clinical laboratory tests will not be performed). In the event of a flare-up or traumatic event, these subjects will receive flare-up based treatment and undergo all flare-up based assessments, including clinical laboratory tests and radiographs if they have not reached 100% skeletal maturity.

- **Subjects from Part B Continuing Non-Flare-Up Based Treatment into Part C**

Subjects who began non-flare-up based treatment during Part B will continue this visit schedule into Part C and will receive non-flare-up based treatment for up to an additional 48 months. Therefore, these subjects may undergo non-flare-up based treatment for up to 72 months over the entire study. These subjects will follow all procedures and undergo all assessments as specified in the Schedule of Assessments in Table 1 of the protocol, including low dose WBCT scan (excluding head) at all annual site visits (Months 12, 24, 36, 48, 60 and 72). Non-flare-up Day 1 is the first day that non-flare-up based treatment was initiated during Part B, and total duration of treatment will continue into Part C.

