3.1.1 Baseline for Non-Flare-up Based Treatment

- For subjects from Part B continuing non-flare-up based treatment into Part C (i.e., subjects who ever received at least one dose of non-flare-up based treatment in both Part B and Part C), baseline

will be based on assessment prior to first non-flare-up treatment in Part B. For subjects who continued from Part B into Part C a Part C baseline is defined as the first assessment in Part C.

- For subjects who did not receive any non-flare-up based treatment in Part B but start non-flare-up based treatment during Part C, baseline will be based on assessment prior to first non-flare-up treatment in Part C.

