PROMIS Global Health T-score and changes from baseline (defined in Section 3.1) will be summarized at each scheduled visit with descriptive statistics. Data from adult (both physical health and mental health) and pediatric forms will be summarized separately.

7 Safety Data

Safety data summaries in the final CSR will be based on the safety data presentations in recent documents, including the Safety Update included in the NDA and the Day 90 Safety Update; the primary difference will be that those summaries included data from all palovarotene studies, while the Study 202 presentations will only include data collected in Study 202.

While the majority of content listed below corresponds to the data presentation in the interim CSR, it is also relevant for pooled summaries that will be the basis for the final CSR safety discussion.

Adverse events will generally be presented by treatment period (See Section 7.1 for classification of treatment periods) and in total for the Enrolled Population.

The Principal Safety Set (Principal SS) includes all enrolled subjects with the R206H ACVR1 mutation receiving at least one dose of palovarotene in the current study.

Safety data for flare-up based treatment assessments will generally be presented by group combined PVO 20/10 mg for the Flare-up Treated Population.

For vitals, labs, ECGs, physical examination, linear growth assessment and CSSR, summary for non-flare-up based treatment assessments (at regular scheduled visits) will be presented by groups: PVO 20/10 mg only, PVO 5 mg, PVO Total and Never Received PVO Treatment using Enrolled Population. The PVO 20/10 mg only group only includes subjects who did not take PVO 5 mg.

Assessments obtained in Part D include yearly linear height, knee height, weight, physical exam, vital signs, radiographic assessments of the knee and hand/wrist, low-dose WBCT imaging excluding head, adverse events, and concomitant medications.

Pregnancy and Teratogenicity Assessment

Pregnancy and pregnancy outcomes will be monitored throughout the study

Pregnancy test results for females of child-bearing potential were provided as subject listings.

A listing of pregnancy and pregnancy outcomes will summarize subject results

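### Part C FOP-PFQ Total: change from baseline runs across the pediatric and adult forms when a subject turns 15, and the rescaling does not correct for their different domain mix

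*SAP*

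**What the plan says.** All references are to the Part C SAP.

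- **Form by age (6.2.3).** "The adult form will be administered to subjects 15 years and older". At ages 8 to 14 both a self-completed and a proxy-completed pediatric form are given, and the proxy form is analysed unless only the self form exists.
- **Items (6.2.3).** "The FOP-PFQ consists of 28 questions on the adult form and 26 questions on the pediatric form scored on a scale from 1 to 5". The Total is the plain sum of all items. The adult form has 15 upper-extremity and 13 mobility items; the pediatric form has 18 and 8.
- **Pooling (6.2.3).** The reason given for rescaling is: "As the analysis for FOP-PFQ will be performed across all subjects (adult and pediatric) and the number of contributing questions differs". Each score becomes (highest − observed) / range, with 0% best and 100% worst.
- **Summary (6.2.3 and 6.2).** Percentages and their changes from the Section 3.1 baseline "will be summarized at each scheduled visit with descriptive statistics", every six months to Month 36. They are also shown before the dosing pause and after restart.
- **Baseline (3.1.1 to 3.1.4).** Baseline is one assessment fixed in time. For subjects continuing non-flare-up treatment from Part B it "will be based on assessment prior to first non-flare-up treatment in Part B". For those starting in Part C it is the assessment before the first such dose in Part C. A restart baseline is defined in 3.1.4. None of these definitions depends on form or respondent.
- **PROMIS, for contrast (6.2.4).** "Data from adult (both physical health and mental health) and pediatric forms will be summarized separately". The pediatric form yields a Total only, yet item 4 of section 6.2 lists "mental function for subjects < 15 years old".

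**The concern.** A change score is meaningful only if both ends measure the same thing. Percentage of worst puts a 26-item and a 28-item sum on a common 0 to 100 range, but it leaves each form's domain weights as they are. In a disease that can affect the upper limbs and the legs unequally, a subject measured on the pediatric form at baseline and on the adult form later can show a change in Total that comes only from reweighting. Its sign depends on which domain is worse affected and has nothing to do with the drug. The respondent may also change at the same moment, from parent proxy to the adult form.

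At stake is the reading of a secondary endpoint in a study of about 60 subjects, where a few shifts of several points could move the mean of a small group. The SAP keeps the adult and pediatric PROMIS forms apart but pools the FOP-PFQ forms.

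**Working it through.** **The plan's own figures.** Table 2 of 6.2.3 uses a 15 to 75 score (range 60). Observed 45, 40, 35, 30 and 25 give 30/60 = 50.0%, 35/60 = 58.3%, 40/60 = 66.7%, 45/60 = 75.0% and 50/60 = 83.3%. All five reproduce. The range is that of the adult Upper Extremities subscore, so the table does not illustrate a change between forms.

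**Inputs (item lists in 6.2.3).**

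| Form | Upper extremity | Mobility | Items | Total range | Mobility weight |
|---|---|---|---|---|---|
| Adult | 15 | 13 | 28 | 28–140 (112) | 13/28 = 46.43% |
| Pediatric | 18 | 8 | 26 | 26–130 (104) | 8/26 = 30.77% |

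The adult lists cover questions 1–28 once each and the pediatric lists cover 1–26 once each. The Total is therefore exactly the two subscores combined.

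**Formula.** Let M and U be the Mobility and Upper Extremities percentages of worst, and w the mobility weight. With complete items, Total% = w × M + (1 − w) × U. If M and U are the same on both forms, switching from pediatric to adult changes the Total by

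(13/28 − 8/26) × (M − U) = 0.1566 × (M − U).

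**Check from raw items.**

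- Upper-limb items all 5, mobility items all 1 (M = 100, U = 0). Pediatric sum 18×5 + 8×1 = 98, so (130 − 98)/104 = 30.77%. Adult sum 15×5 + 13×1 = 88, so (140 − 88)/112 = 46.43%. Shift +15.66.
- The reverse pattern (M = 0, U = 100) goes from 69.23% to 53.57%. Shift −15.66.
- Upper-limb items all 4, mobility items all 2 (M = 75, U = 25). Pediatric 42/104 = 40.38%; adult 54/112 = 48.21%. Shift +7.83.

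**Range over assumed domain gaps** (the SAP gives no domain scores):

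| M | U | Gap | Shift in Total |
|---|---|---|---|
| 50 | 50 | 0 | 0 |
| 60 | 50 | 10 | +1.57 |
| 60 | 40 | 20 | +3.13 |
| 75 | 25 | 50 | +7.83 |
| 100 | 0 | 100 | +15.66 |

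**Who can cross.** Only subjects under 15 at baseline who turn 15 by the visit. For those starting non-flare-up treatment in Part C, the endpoint runs to Month 36. Section 2.3 says treatment is not restarted under 14, so measured from the 3.1.4 restart baseline only subjects aged 14 at restart can cross, and they do so within 12 months. The effect on a group mean is the fraction of subjects who have crossed times their average shift. The SAP gives neither quantity.

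**Under the fix.** For same-form pairs w is constant, so the weighting shift is 0.

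**The case against.** **Cross-form subtraction is inferred.** No sentence says that a pediatric baseline is subtracted from an adult-form visit, and the questionnaires sit in protocol appendices not shown. This is fair. But form by age, pooled forms, a fixed baseline and no switching rule lead a programmer to that subtraction. Reading the age limit as age at enrolment would avoid it, but the text does not say so.

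**The effect is usually small.** This stands. A shift of 15.7 needs one domain at its best and the other at its worst. It concerns the Total only; the Upper Extremities and Mobility percentages are also available and are not moved by weighting.

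**Reach.** A reader might infer that many subjects cross, because "these subjects may undergo non-flare-up based treatment for up to 72 months over the entire study". The documents do not support this. That horizon belongs to subjects who began non-flare-up treatment in Part B. The Part B SAP scheduled that treatment for the Adult Cohort, defined by at least 90% skeletal maturity. The definition is regardless of age, so crossing is possible, but these are the subjects least likely to have a pediatric-form baseline. No count of crossers is given.

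**PROMIS.** A reader might extend the same fault to PROMIS. Section 6.2.4 already summarizes the forms separately, so no mixed-form change enters the means. Nor do the different self and proxy T-scores at the same raw score in Table 10 (0.9 to 3.4 points, mean 2.3) measure a respondent bias. Separate conversion tables give different T-scores by construction.

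**Consequence.** The endpoint is secondary and descriptive; the inferential comparisons in section 3.4 concern new HO. This limits the weight of the point but does not make the change score correct.

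**Conclusion.** The point holds for the FOP-PFQ Total in Part C. Applied as written, section 6.2.3 gives a subject who turns 15 a change in Total of 0.157 × (Mobility% − Upper Extremities%) with no change in function in either domain. That is about 1.6 to 7.8 points for assumed gaps of 10 to 50 points, in either direction, with 15.7 as a ceiling and not an expected value.

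The result assumes that the two domain percentages are equal on both forms and that items are complete. Differences in item content, or a change from proxy to self-report, could add a further shift that cannot be sized from the SAP. The number affected is unknown, so the effect on group means is unknown too. The SAP should be corrected here, but the point does not touch the primary endpoint.

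Separately, item 4 of section 6.2 does not match 6.2.4: mental function under 15 cannot be produced from a form that yields only a Total. This is a small wording error.

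**What to change.** 1. In 6.2.3, include FOP-PFQ Total change from baseline in the summaries only when baseline and visit use the same form and, within the pediatric form, the same respondent.
2. List cross-form values separately and flag them.
3. If change from the first adult-form visit is wanted, keep it as a separate supportive listing. That visit is usually on treatment, so it should not be pooled with pre-treatment baselines.
4. In item 4 of section 6.2, name the pediatric PROMIS endpoint as the global health Total score, in line with 6.2.4.

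The cost is SAP wording and minor programming, with no new data. The downside is fewer Total change values for subjects who cross age 15, most noticeably at later visits. Reporting the number excluded at each visit would make that loss visible and supply the count of crossers that the SAP lacks.

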6.2.4 PROMIS Global Health

An age-appropriate form of the PROMIS Global Health short form will be administered to subjects (or parent proxy). The adult form will be administered to subjects 15 years and older. For subjects between 8 and 14 years of age, both the pediatric self-completed and the pediatric proxy-completed forms will be administered. The proxy-completed form will be used for analysis unless only the self-completed form is available.

The PROMIS Global Health short form consists of 10 questions on the adult form and nine questions on the pediatric form scored on varying scales. The questions are described in detail in Appendices 8A, 8B, and 8C of the protocol.

For the adult form, Global Physical Health and Global Mental Health scores will be calculated. The Global Physical Health score will be calculated as the sum of scores from questions 3, 6, 7, and 8, and will range from 4 (worse health) to 20 (better health). The Global Mental Health score will be calculated as the sum of scores from questions 2, 4, 5, and 10, and will range from 4 (worse health) to 20 (better health). In the calculation of the Global Physical Health and Global Mental Health scores, the following questions will be rescaled as shown in Table 3.

Table 3: Rescaled PROMIS Global Health Scale Scores

Question(s)	Score	Rescaled Score
7	0	5
	1-3	4
	4-6	3
	7-9	2
	10	1
8 and 10	1	5
	2	4
	3	3
	4	2
	5	1

If a subject is missing any of the contributing scores, the Global Physical Health or Global Mental Health score will not be calculated.

For the pediatric form, only a Total score will be calculated as the sum of scores from the first seven questions and will range from 7 (worse health) to 35 (better health). If a subject is missing some (but not more than three) of the contributing question scores, the Total score will be calculated as the average observed score multiplied by the number of expected question scores. For example, the Total score would be calculated as the average of the non-missing scores x 7. The proxy-completed PROMIS form will be used for analyses unless only the self-completed form is available.

Global Physical Health scores and Global Mental Health scores will also be converted to T-scores as described in detail in [Appendix 1](#). A T-score of 50 is normal and increments of 10 +/- 1 standard deviation away from the norm. A T-score <50 indicates worse health, while a T-score >50 indicates better health. Note that higher values indicate better health.

PROMIS Global Health T-score and changes from baseline (defined in Section 3.1) will be summarized at each scheduled visit with descriptive statistics. Data from adult (both physical health and mental health) and pediatric forms will be summarized separately.

7 Safety Data

Safety data summaries in the final CSR will be based on the safety data presentations in recent documents, including the Safety Update included in the NDA and the Day 90 Safety Update; the primary difference will be that those summaries included data from all palovarotene studies, while the Study 202 presentations will only include data collected in Study 202.

While the majority of content listed below corresponds to the data presentation in the interim CSR, it is also relevant for pooled summaries that will be the basis for the final CSR safety discussion.

Adverse events will generally be presented by treatment period (See Section 7.1 for classification of treatment periods) and in total for the Enrolled Population.

The Principal Safety Set (Principal SS) includes all enrolled subjects with the R206H ACVR1 mutation receiving at least one dose of palovarotene in the current study.

Safety data for flare-up based treatment assessments will generally be presented by group combined PVO 20/10 mg for the Flare-up Treated Population.

For vitals, labs, ECGs, physical examination, linear growth assessment and CSSR, summary for non-flare-up based treatment assessments (at regular scheduled visits) will be presented by groups: PVO 20/10 mg only, PVO 5 mg, PVO Total and Never Received PVO Treatment using Enrolled Population. The PVO 20/10 mg only group only includes subjects who did not take PVO 5 mg.

Assessments obtained in Part D include yearly linear height, knee height, weight, physical exam, vital signs, radiographic assessments of the knee and hand/wrist, low-dose WBCT imaging excluding head, adverse events, and concomitant medications.

Pregnancy and Teratogenicity Assessment

Pregnancy and pregnancy outcomes will be monitored throughout the study

Pregnancy test results for females of child-bearing potential were provided as subject listings.

A listing of pregnancy and pregnancy outcomes will summarize subject results

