13 APPENDIX

Appendix 1. PROMIS T-Score Conversions

The following conversion tables allow a user to convert Global Physical Health, Global Mental Health, and Total scores into T-scores. T-score distributions are standardized such that a 50 represents the average (mean) for the US general population, and the standard deviation around that mean is 10 points. A high score always represents more of the concept being measured. Thus, a subject who has a T-score of 60 is one standard deviation better (healthier) than the general population.

Table 9: PROMIS T-Score Conversions for Adult Global Physical and Mental Health

Adult Global Physical Health			Adult Global Mental Health		
Raw Score	T-Score	Standard Error	Raw Score	T-Score	Standard Error
4	16.2	4.8	4	21.2	4.6
5	19.9	4.7	5	25.1	4.1
6	23.5	4.5	6	28.4	3.9
7	26.7	4.3	7	31.3	3.7
8	29.6	4.2	8	33.8	3.7
9	32.4	4.2	9	36.3	3.7
10	34.9	4.1	10	38.8	3.6
11	37.4	4.1	11	41.1	3.6
12	39.8	4.1	12	43.5	3.6
13	42.3	4.2	13	45.8	3.6
14	44.9	4.3	14	48.3	3.7
15	47.7	4.4	15	50.8	3.7
16	50.8	4.6	16	53.3	3.7
17	54.1	4.7	17	56	3.8
18	57.7	4.9	18	59	3.9
19	61.9	5.2	19	62.5	4.2
20	67.7	5.9	20	67.6	5.3

Table 10: PROMIS T-Score Conversions for Pediatric Global Health

Pediatric Self-Completed Total			Pediatric Proxy-Completed Total		
Raw Score	T-Score	Standard Error	Raw Score	T-Score	Standard Error
7	16	3.4	7	14.7	2.9
8	17.1	3.6	8	15.3	3.1
9	18.3	3.7	9	16	3.2
10	19.7	3.8	10	16.9	3.4
11	21.2	3.8	11	18.1	3.6
12	22.8	3.7	12	19.4	3.7
13	24.4	3.6	13	21	3.8
14	26.1	3.6	14	22.7	3.8
15	27.6	3.5	15	24.4	3.7
16	29.2	3.5	16	26.1	3.7
17	30.8	3.5	17	27.7	3.7
18	32.4	3.6	18	29.4	3.8
19	34	3.6	19	31.2	3.8
20	35.6	3.6	20	32.9	3.8
21	37.2	3.6	21	34.6	3.8
22	38.8	3.6	22	36.2	3.8
23	40.4	3.6	23	37.9	3.9
24	42.1	3.7	24	39.7	4
25	43.9	3.7	25	41.7	4
26	45.7	3.6	26	43.6	3.9
27	47.5	3.6	27	45.4	3.8
28	49.2	3.6	28	47.3	3.9
29	51.1	3.7	29	49.3	4.1
30	53.3	3.9	30	51.8	4.4
31	55.7	4.2	31	54.5	4.7
32	58.3	4.5	32	57.3	5
33	61.1	4.9	33	60.2	5.4
34	64.2	5.4	34	63.2	6
35	67.5	6.1	35	66.1	6.5

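### Pediatric PROMIS and FOP-PFQ change scores can pair a parent's rating with a child's, because the proxy-first rule does not hold the reporter constant between baseline and follow-up

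*SAP*

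**What the plan says.** Part C SAP 6.2.4 (PROMIS Global Health) provides for two reporters: "For subjects between 8 and 14 years of age, both the pediatric self-completed and the pediatric proxy-completed forms will be administered". The form for analysis is chosen by availability: "The proxy-completed form will be used for analysis unless only the self-completed form is available". The section repeats the rule later: "The proxy-completed PROMIS form will be used for analyses unless only the self-completed form is available". Section 6.2.3 (FOP-PFQ) has the same sentence: "The proxy-completed form will be used for analyses unless only the self-completed form is available".

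The endpoint is change. Section 6.2 lists change from baseline using "age-appropriate forms of the PROMIS Global Health Scale at Months 6, 12, 18, 24, 30, and 36", and FOP-PFQ at the same months. Section 6.2.4 adds: "PROMIS Global Health T-score and changes from baseline (defined in Section 3.1) will be summarized at each scheduled visit with descriptive statistics". The only separation of forms is by age group: "Data from adult (both physical health and mental health) and pediatric forms will be summarized separately".

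Appendix 1, Table 10 ("PROMIS T-Score Conversions for Pediatric Global Health") converts raw totals with one column for the self form and another for the proxy form.

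The same selection rule stands in the Part A SAP (7.2.8 and 7.2.9) and the Part B SAP (6.2.9 and 6.2.10).

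**The concern.** A change score is interpretable when the same instrument, answered by the same kind of reporter, is used at both ends. An availability rule does not secure that. If the parent completed the form at baseline but only the child did at Month 12, the rule takes the parent's score first and the child's score second. The difference then contains true change, any parent-child difference in rating and, for PROMIS, the difference between two conversion tables. The reverse sequence has the same defect with the opposite sign.

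The summary tables would not reveal this, because pediatric self and proxy forms are reported together. Part C has about 60 subjects in all (Section 2.4), and those aged 8 to 14 are only some of them, so a visit mean may rest on few children.

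**Working it through.** **Does any other rule hold the reporter constant?** The relevant Part C sections are:

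- Section 3.1 (baseline) fixes which assessment is baseline, not who completed it. For subjects continuing non-flare-up treatment from Part B, baseline is the assessment before the first such dose in Part B, so the two forms can be years apart.
- Section 3.5 (missing data) uses observed data only. It says nothing about a missing proxy form when the self form is present.
- Sections 6.2.3 and 6.2.4 choose between forms but do not say whether the choice is made once per subject or at each visit. For forms given at every visit, a choice at each visit is the natural reading.

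No section closes the gap.

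**Are the two pediatric PROMIS forms on a common footing?** The inputs are the self and proxy T-scores in Part C Table 10 for all 29 raw totals from 7 to 35. The formula is gap(r) = T_self(r) − T_proxy(r). Selected rows:

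| Raw total | Self T | Proxy T | Gap |
|---|---|---|---|
| 7 | 16.0 | 14.7 | 1.3 |
| 12 | 22.8 | 19.4 | 3.4 |
| 13 | 24.4 | 21.0 | 3.4 |
| 14 | 26.1 | 22.7 | 3.4 |
| 21 | 37.2 | 34.6 | 2.6 |
| 28 | 49.2 | 47.3 | 1.9 |
| 33 | 61.1 | 60.2 | 0.9 |
| 35 | 67.5 | 66.1 | 1.4 |

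Over all 29 totals the gap is always positive: minimum 0.9 (raw 33), maximum 3.4 (raw 12 to 14), mean 2.30, median 2.4. With an unchanged raw total, a proxy baseline followed by a self form reads as an improvement of 0.9 to 3.4 points. The reverse order reads as a worsening of the same size.

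**What could this do to a mean change?** The documents give no switching rate, so the share f is an assumption. If f of the subjects switch in one direction at the same raw total, shift = f × gap:

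| Assumed f | Gap 0.9 | Gap 2.30 | Gap 3.4 |
|---|---|---|---|
| 5% | 0.05 | 0.11 | 0.17 |
| 10% | 0.09 | 0.23 | 0.34 |
| 20% | 0.18 | 0.46 | 0.68 |
| 30% | 0.27 | 0.69 | 1.02 |

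Switches in opposite directions would partly cancel in the mean.

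**FOP-PFQ.** There are no separate self and proxy conversions, so Table 10 has no bearing here. On the 26-item pediatric total, one raw point is 100 / (26 × 4) = 0.96 percentage points of worst score. Any parent-child difference passes straight into the change, but the documents give no figure for that difference.

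**The case against.** The best case against the point has four parts.

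- **The level is not written.** A reader might take the plan to state that the form is chosen visit by visit. It does not; that is inferred from silence. The inference is natural, and a programmer could implement either version, so the wording needs fixing on either reading.
- **The table gap is not an error estimate.** A reader might infer that switching alone biases change by up to 3.4 points, about a third of the 10-point standard deviation. The documents do not support this. Each column belongs to its own reporter, and nothing says a parent and child rating the same health reach the same raw total. Real disagreement could offset the gap or add to it. The figure also concerns one subject, not a group mean. The gap is below the tabulated standard error of both forms at every raw total (raw 13: gap 3.4, standard errors 3.6 and 3.8). That comparison does not remove the point, because measurement error averages out over subjects and one-directional switching does not.
- **The trigger is narrow.** It needs the proxy form missing and the self form present at one of the two visits, and Section 3.5 expects little missing data. For post-restart summaries, Section 2.3 rules out restarting under age 14 and Section 3.1.4 sets a restart baseline, so at that baseline the two-form rule reaches only 14-year-olds. This stands and limits the likely size.
- **A same-reporter rule could do harm.** Applied without limit, it would remove later FOP-PFQ change scores for children with a proxy baseline who turn 15 and answer the adult form themselves, although Section 6.2.3 rescales scores so that adult and pediatric forms can be analysed together. This stands, and the remedy must be confined to pairs of pediatric forms.

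Part C 6.2.4 also names only the Global Physical and Mental scores for T-score conversion. But Table 10 supplies the pediatric conversion, and the Part A and Part B SAPs convert the pediatric Total explicitly, so the point does not turn on that wording.

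**Conclusion.** The point holds as a minor one. As written, the rule permits change from baseline to be taken across two reporters, and the plan itself scores those reporters' PROMIS forms on different tables.

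The supportable size is a gap of 0.9 to 3.4 T-score points at equal raw totals, as an illustration that the forms are not interchangeable. The corresponding shift in mean change is about 0.05 to 1.0 points, on the assumptions that 5% to 30% switch in one direction and that raw totals stay equal. For FOP-PFQ the mixing is the same and its size is unknown.

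A reader might go further and conclude that the shift rivals a treatment effect. The documents give no effect size for these questionnaires, no count of subjects aged 8 to 14 and no switching rate, so that conclusion has no basis. The endpoints are secondary and summarized descriptively.

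**What to change.** In Part C SAP 6.2.3 and 6.2.4, add that when baseline and follow-up are both pediatric forms, change is computed only from same-reporter pairs: proxy with proxy if a proxy baseline exists, otherwise self with self. List mixed-reporter pairs separately. Leave the planned handling of the move to the adult form at age 15 as it is.

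Parts A and B were already summarized in the interim report, and Part C SAP Section 1.1 does not intend to rerun such tables. For those parts, flag any mixed-reporter pairs and do not require tables to be rerun.

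The cost in Part C is a sentence and a selection rule per questionnaire, using forms already collected. Some change scores become missing, chiefly where a proxy baseline exists and the later proxy form does not. In exchange, the conversion gap at an unchanged raw total is zero by construction.
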